Technology Enhanced Family-Focused Treatment

Statistical Analysis Plan

Document number: NCT03913013

March 16, 2023

Date: March 16, 2023

Statistical Analysis Plan

The study hypotheses centered on the evolution from baseline to 9, 18 and 27 weeks of mean PSR depressive symptoms (primary study outcome), and secondarily, SCARED anxiety scores and CGAS functioning scores, calculated for each interval and compared across treatment conditions using linear and generalized linear mixed models (PROC MIXED and GLIMMIX, Statistical Analysis System [SAS], V 9.4). Mixed models, calculated using all available data, account for correlations induced by repeated measurements within subjects and produce unbiased estimates of missing data, assuming observations are missing at random. The models used treatment group (FFT-MCC vs. FFT-Track) and study visit (0, 9 weeks, 18 weeks, and 27 weeks) as fixed effects and participant as a random effect. Sensitivity analyses redefined mixed models to instead covary for baseline scores and to examine the effects of outliers (see online supplement).

Secondary models examined three-way interactions between treatment, study visit (baseline score and 9-, 18- and 27-week scores), and primary mood diagnoses (depressive vs. bipolar spectrum disorder) or comorbid disorders (presence/absence of ADHD or anxiety disorders) on the repeated dependent variables (depression [primary], anxiety, and global functioning [secondary]). Age, sex, parent diagnoses, and baseline parent-rated CALS mood instability scores were included as covariates. For outcomes measured at four time points in 60 study completers, we had 80% power to detect an overall group by study visit interaction corresponding to a treatment effect size of $f^2 = .03$, just above Cohen's threshold for a small effect ($f^2 = .02$). Because of the exploratory nature of the study, we did not correct for multiple comparisons.

In exploratory analyses, we compared treatment groups on app engagement (frequency of adolescents' and parents' weekly app check-ins), using scaled Poisson regression models (PROC GENMOD in SAS) to account for the skewed distribution of check-in counts. Goodness of fit tests indicated no evidence of overdispersion (Pearson χ^2 , $p=0.5$, deviance $p=0.3$). Within the FFT-MCC group, we used Spearman rank-order correlations to examine whether the proportion of weeks in which adolescents reported use of an FFT skill on the app were associated with changes in PSR depression scores over 27 weeks.

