Participants in phase 1 (N = 25) and phase 2 (N=60) will be boys and girls (ages 13-19 yrs) who have high mood instability scores, at least one parent with a history of BD or MDD, and at least one parent rated high in Perceived Criticism, a 1-10 child- and parent-rated scale that is a proxy measure for expressed emotion (EE). Each family will receive 12 FFT sessions in 18 weeks, with assessments of EE, mood instability, and symptoms/functional outcomes at intake, mid-treatment, post-treatment (18 wks.) and follow-up (27 wks.). At study entry, all participants will be given access to the MyCoachConnect (MCC) smartphone app with an interactive voice-response (IVR) system. In phase 1, all participants (adolescents and parents) will receive FFT and the fully functional MyCoachConnect (MCC) app. In phase 2, participants will be randomly assigned in a 1:1 split to:

(1) **FFT with the full MCC app (FFT-MCC)**, consisting of instructions for daily mood, sleep and family functioning ratings, how to use FFT skills (e.g., symptom tracking, active listening, problem-solving), and how to log efforts to practice these skills; instructional videotapes showing how the skills are used in practice; and weekly and standard interval (every 9 week) assessments completed by the participant on the app. The clinical provider, via the MCC app, will send tailored alerts to parents and youth about mood management strategies and pertinent communication skills for resolving conflicts, which they can practice between sessions. All participants (adolescents, parents) will be instructed to call the automated voice system twice per week and leave a 3-5 minute speech sample surveying how they are doing and how they are getting along with their child (or parent).

(2) **FFT with the Assessment App (FFT-ASSESS)**, the same 12 sessions of FFT will be given, but with a scaled-down version of the app consisting of weekly questionnaires to be rated and call-in instructions, plus standard interval (every 9 week) questionnaire assessments. There will be no educational or skill-oriented coaching of participants by clinicians via the app. However, families will still receive the standardized course of 12 sessions/ 4 months of FFT, which is more than families with children with mood disorders ordinarily receive in the community.

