Aim 2 (Phase 2): *Using in-person assessments of moods and EE at baseline, 9, 18, and 27 weeks, and MCC speech samples obtained weekly, we will determine whether targets and outcomes improve over time, and whether these improvements occur to a greater extent in FFT-MCC than in FFT-ASSESS.*

Hyp 2a. We will observe significant improvements over 27 weeks on dichotomous (high vs. low) and dimensional (number of criticisms) ratings of EE and mood instability (targets), and in the clinical outcomes of mood severity and quality of life. These improvements will be greater in FFT-MCC than in FFT-ASSESS. We predict that targets and clinical outcomes will be correlated over time, and that bigger changes in targets will be predictive of larger clinical improvements.

Hyp 2b. In both treatment conditions, we will find prognostic relationships between speech features (collected in call-ins to the voice app) and concurrent or later depression and suicide risk. We do not expect that suicide risk will change more in one MCC condition than in the other.

To more fully investigate hypothesis 2b, we will add two measures to our standard interval assessment (conducted every 9 weeks for 27 weeks) to assess suicide risk: the Suicidal Ideation Questionnaire-Junior (SIQ-Jr) (Reynolds, 1998 #1106) and the Columbia-Suicide Severity Rating Scale (Posner, 2009 #2158). We will explore both population-based training as well as within-person training to create personalized prediction models of suicide risk using

machine learning. Because we are collecting speech samples and suicide risk measures over a 6-month (27 week) period, we will be able to conduct analyses to explore the temporal dynamics of suicide risk. This includes understanding prior speech sampling as predictors of change in suicidal ideation or behaviors within and across individuals over time.

Participant eligibility (both study phases)

The **eligibility criteria** for this study are:

- (1) The family is English-speaking (although English need not be their first language);
- (2) The index adolescent is age 13 years, 0 mos. – 19 years, 11 mos.;
- (3) at least one parent has received a lifetime diagnosis of bipolar I or II disorder or major depressive disorder by the *MINI International Neuropsychiatric Interview*. The protocol does not require participation of this parent in treatment;

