Adolescent: Once the parents and youth have signed the consent and assent forms, a research assistant (independent evaluator) will administer to the child the MINI International Neuropsychiatric Interview for DSM-5 diagnoses, the Young Mania Rating Scale, the Children's Depression Rating Scale, the AUS/DUS substance use measure, and the Adolescent Longitudinal Interval Follow-up Interview (A-LIFE) covering the 18 weeks prior to the study. A separate research assistant will administer these measures with the parent so that consensus judgements can be made. The interviews will be audio recorded (see Confidentiality sections, below). Based on both sources of information, the independent evaluator will characterize each week of the 18 weeks prior to intake using the 1-6 A-LIFE Psychiatric Status Ratings of depression, mania, hypomania and suicidal ideation/behavior. These are standard structured interviews and will take approximately 1 to 1.5 hours per person. The adolescent will be allowed to take as many breaks as s/he needs, and the interview can be split into two appointments if preferred. Both parents will fill out the PGBI-10M, and both parents and the child will complete the Children's Affective Lability Scale (CALS), with separate versions for each.

Parents: Study children must have at least one parent who has a lifetime diagnosis of bipolar I or II disorder or major depressive disorder by the MINI (adult version) for DSM-5. If there are two biological parents, we will individually interview each parent with the MINI regarding their own psychiatric history to verify that the child has at least one parent with lifetime major depression or bipolar disorder. Adolescents will only be eligible if we can interview at least one parent(s) directly. If the second parent is deceased or otherwise unavailable, we will obtain information about him or her using the other parent's report, with questions guided by the Family History Screen (Weissman et al., 2000) and diagnoses based on DSM-5. However, in these cases we will only include the adolescent/family if the first parent has given sufficient examples to make an unequivocal diagnosis of lifetime mood disorder in the second parent (i.e. ratings of 'probable' or 'definite' on the Family History Screen).

Expressed Emotion (EE) from Five-Minute Speech Sample interviews

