The data to be collected for this study are based on:

- (1) individual structured interviews (by an independent evaluator)
- (2) paper and pencil questionnaires, and
- (3) MyCoachConnect (MCC) mobile phone app with an interactive voice system that enables users to leave speech samples or complete standardized questionnaires.

Most of the measures have been used before in our studies of childhood mood disorders. Table 1 describes all instruments and their timing. Standardized measures (for example, parental EE, Perceived Criticism Measure, child's mood instability) will be administered at baseline, mid-treatment (9 weeks), 18 weeks (end of treatment) and 27 weeks post-baseline (hereafter called *standard study intervals*). The interview-based measures of clinical progress (ALIFE Psychiatric Status Ratings, CDRS, and YMRS) are based on a consensus between child and parent reports from direct interviews administered every 9 weeks. We will utilize the MCC app to collect self-report ratings by parents and teens. In the FFT-MCC condition, these ratings will be obtained daily and weekly, as explained below. In the FFT-Assess condition, they will be weekly only.

TABLE 1: Longitudinal Assessment Instruments

Clinical State	Construct	Respondent	Timeline
Mood Rating (5 items)	Current Mood	Child	Daily (FFT-MCC only); weekly (FFT-Assess)
Sleep (sleep/wake times, quality)	Sleep disruption	Child	Daily (FFT-MCC only), weekly (FFT-Assess)
Patient Health Q'nnaire-9, PHQ-9	Depression Symptoms	Child	Stand. interval; weekly
Children's Affective Lability Scale (CALS)	Mood Instability	Child; parent	Stand. interval; weekly
ADHD Rating Scale	ADHD	Parent re: child	Baseline only
Modified Overt Aggression Scale	Aggression	Parent re: child	Standard int.; weekly
Parental General Behavior Inv. 10M	Mood & energy regulation	Parent re: self	Standard int.
Parental 7-Up 7-Down questionnaire	Depressed and manic mood states	Parent Re: child	Standard Int.
Autism Spectrum Disorder Scale	Autism Symptoms	Parent re: child	Baseline only
Children's Depression Rating Scale (CDRS)	Depressive Symptoms	Parent/child consensus	Standard int.
Young Mania Rating Scale (YMRS)	Mania Symptoms	Parent and child	Standard int.

Screen for Children's Anxiety and Related Disorders (SCARED) questionnaire	Anxiety, panic, worry	Child	Standard int.
Adolescent Longitudinal Interval Follow-up (interview)	Depression, hypo/mania, suicidal ideation, psychosis	Parent and child consensus	Standard int.

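### The primary mixed model treats week 0 as an outcome and leaves adjustment for the baseline score to a sensitivity analysis: valid, but inefficient with 60 participants

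*SAP*

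**What the plan says.** The first paragraph of the SAP says the hypotheses concern the "evolution from baseline to 9, 18 and 27 weeks of mean PSR depressive symptoms (primary study outcome"). The main models use treatment group and "study visit (0, 9 weeks, 18 weeks, and 27 weeks) as fixed effects and participant as a random effect". Week-0 PSR is therefore one of four repeated outcomes, and no common baseline mean is imposed. The next sentence but one moves baseline adjustment to a secondary role: "Sensitivity analyses redefined mixed models to instead covary for baseline scores and to examine the effects of outliers".

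The second paragraph lists age, sex, parent diagnoses and baseline parent-rated CALS as covariates; baseline PSR is not among them. The powered test is given as "80% power to detect an overall group by study visit interaction", for 60 completers at four time points and f² = .03. The group-by-visit term is not named among the primary fixed effects, so it is inferred from this sentence. The SAP does not say whether visit is categorical, and it gives no alpha and no within-person correlation.

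In the protocol, the Abstract says that in phase 2 "participants will be randomly assigned in a 1:1 split", and Hypothesis 2a predicts: "We will observe significant improvements over 27 weeks". Under Diagnostic Interviews, the evaluator will "characterize each week of the 18 weeks prior to intake using the 1-6 A-LIFE Psychiatric Status Ratings", while follow-up assessments are nine weeks apart.

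**The concern.** Randomisation makes the arms' baseline means equal in expectation. A model that estimates them separately bases each treatment contrast on change from a noisy baseline and carries that noise into the result. Using the baseline score as a covariate, or constraining the two baseline means to be equal, removes it. The listed covariates do not do this job: entered as main effects, with complete data, they leave within-person contrasts unchanged.

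A second, conditional point is the rating window. Baseline PSR is rated over 18 weeks and follow-up visits are 9 weeks apart, and the SAP does not say which window the week-0 mean uses. If the windows differ, week 0 may not have the same variance as the later outcomes. A random-intercept model with week 0 as an outcome relies on that equality; a covariate does not.

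At stake is whether a trial of 60 leads with the weaker of two valid analyses.

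**Working it through.** **Inputs.** From the documents: N = 60, 1:1 allocation (so 30 per arm), visits at weeks 0, 9, 18 and 27, f² = .03, stated power 80%. Assumed because not given: two-sided alpha 0.05, SD 1, complete data, compound symmetry with correlation rho = 0.3, 0.5, 0.7, and the effect patterns below.

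**The SAP's own figure.** For a 3-df repeated-measures interaction, lambda = f² × N × 4/(1 − rho) = 0.03 × 60 × 4/(1 − rho) = 7.2/(1 − rho), tested on F(3,174). Power is 59% at rho 0, 76% at 0.3, 90% at 0.5 and 99% at 0.7. Reaching 80% needs lambda = 11.15, so rho = 1 − 7.2/11.15 = 0.35. The stated 80% is therefore attainable but cannot be confirmed, because rho is not given.

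**One visit.** The week-27 contrast has variance (4/60) × 2(1 − rho) without adjustment and (4/60) × (1 − rho²) with it. The ratio is 2/(1 + rho) = 1.54, 1.33, 1.18. Sixty unadjusted participants thus give the precision of 60/ratio = 39, 45, 51 adjusted ones. The constrained-baseline model has the same week-27 variance as the covariate model (0.0607, 0.0500, 0.0340).

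**Joint test.** Let d_t be the arm difference at visit t (zero at week 0) and dbar the mean of the three follow-up differences.

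- Interaction as planned: lambda = 15 × SS(d_0, d_9, d_18, d_27 about their mean)/(1 − rho), F(3,174).
- Baseline-adjusted joint test: lambda = 15 × [3 dbar²/((1 − rho)(1 + 3 rho)) + SS(d_9, d_18, d_27 about dbar)/(1 − rho)], F(3,171).

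Example, constant 0.6 SD at rho 0.5:

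- Planned: SS = 3 × 0.36 × (1/4) = 0.27, so lambda = 15 × 0.27/0.5 = 8.1.
- Adjusted: 15 × 3 × 0.36/(0.5 × 2.5) = 12.96.
- Power: 65% against 86%.

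| Pattern (weeks 9/18/27) | Planned, rho .3/.5/.7 | Adjusted, rho .3/.5/.7 |
|---|---|---|
| Linear to 0.7 SD | 50/65/88% | 74/80/93% |
| Constant 0.6 SD | 49/65/88% | 84/86/95% |
| Fading 0.6/0.6/0.3 SD | 46/61/84% | 74/79/91% |
| Late only 0/0/0.6 SD | 49/65/88% | 54/68/89% |

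The linear effect detectable with 80% power falls from 0.97 to 0.75, 0.82 to 0.70 and 0.634 to 0.585 SD.

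**Other assumptions.**

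- Visit as a linear term (1 df), linear 0.7 SD: 67/81/96% becomes 87/91/98%.
- AR(1), rho 0.5: linear 37% to 64%, constant 51% to 79%.
- Baseline variance 0.7 of follow-up, rho 0.5: linear 72% to 80%, constant 76% to 86%.
- F(3,57) in place of F(3,171): adjusted power about 1 to 2 points lower.
- Simulation with estimated variances and F(3,57), 4,000 runs per rho: adjusted type I error 4.5/4.6/4.7%; adjusted power 71/78/91% (linear) and 82/83/94% (constant).
- A separate simulation of the week-27 contrast: both analyses unbiased, type I error 4.6 to 5.7%.

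**A trap in the replacement.** With baseline as covariate and three follow-up visits, the group-by-visit interaction has 2 df and lambda = 15 × SS(d_9, d_18, d_27 about dbar)/(1 − rho). Its power is 5% for a constant effect and 25/34/53% for the linear one. The treatment test must therefore be the joint test of the three arm differences.

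**The case against.** The strongest reply is that nothing is wrong with the plan. The interaction test is valid and directly expresses a hypothesis about change from baseline, the study is described as exploratory, and the adjusted model was already fitted. Only its rank is in dispute, and the supplement, which is not available here, may already report what is asked for. Promoting a sensitivity model in a SAP dated March 2023 that already reports a model-fit result also invites selection by outcome.

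Much of this stands. The issue is precision, and the promoted analysis cannot be called prespecified. It does not follow that the less precise analysis should lead: the joint follow-up test addresses the same 27-week course.

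The size also rests on unknowns. At rho 0.8 the gain is only about 1 point (linear), 2 (constant and fading) and 0 (late only). For a late-only benefit with the conservative F(3,57), adjusted power is 52/66/87% against 49/65/88%, so the gain disappears at rho 0.7. On matched degrees of freedom about 1 point remains, and adjusted lambda was larger in every case checked.

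The window point is conditional, since no document says week 0 averages all 18 weeks. A lower baseline variance would reduce the gain: at rho 0.5, from 15 to 8 points (linear) and from 21 to 10 (constant). A random participant effect also does not exclude a further residual covariance structure.

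**Conclusion.** The concern holds. The main analysis is unbiased with near-nominal type I error, but it gives up precision that a baseline value already collected would supply. Under compound symmetry with 30 per arm and complete data, the loss at rho 0.5 is about 15 power points for a linear 0.7 SD benefit, 21 for a constant 0.6 SD benefit, 18 for a fading one and 3 for a late-only one. The losses are larger at rho 0.3 and smaller at 0.7. Rho, alpha and the effect pattern are assumptions, so the direction is firmer than the size. Confidence is medium. The change should be made, but its absence does not invalidate the trial.

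**What to change.** Make the baseline-adjusted mixed model the main analysis, in one of two forms: outcomes at 9, 18 and 27 weeks with the baseline score as covariate, or all four visits with the two baseline means constrained equal and an unstructured covariance. The second also keeps participants who have only a baseline value. State whether the listed covariates stay in the model, and which window the week-0 PSR mean uses.

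Test the arm differences at weeks 9, 18 and 27 jointly, and report the adjusted difference with its confidence interval at each visit. Do not rely on the 2-df interaction alone. A 1-df contrast (week 27 or the follow-up mean) may be added to show direction, but it gains power only if it matches the pattern. Treatment ends at week 18, and at rho 0.5 week 27 alone has 26% power for 0.6/0.6/0.3 SD; for a benefit gone by then it has 5%.

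The cost is added output: baseline PSR is collected and the covariate model has been fitted. The real cost is in status. The adjusted analysis must be labelled as specified later and shown beside the interaction test.
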